Use of TXA in Urologic literature has been limited. One prospective, randomized controlled trial studied the use of TXA in 40 men undergoing transurethral resection of the prostate (TURP).⁸ The authors found that TXA resulted in significantly less postoperative serum hemoglobin drop, less hemoglobin loss per gram of resected tissue, shorter OR time, and more resected tissue.⁸ In another prospective, randomized controlled trial, the authors randomized 136 men undergoing TURP to receiving TXA or not.⁹ The authors found TXA resulted in reduced operative blood loss, the amount of blood loss per gram of resected tissue, and shorter OR time. Interestingly, TXA did not decrease length of stay or catheter duration.⁹ In one systematic review analyzing the effects of TXA after transurethral resection of the prostate, the authors included nine studies in their meta-analysis and found that TXA reduced intraoperative estimated blood loss as well as the transfusion rate.¹⁰ The use of TXA in percutaneous nephrolithotomy (PCNL) has also been studied. A randomized, double-blinded, placebo-controlled trial enrolled 192 patients with Guy's stone scores III-IV. Patients were given 1g of IV TXA vs. placebo at time of anesthetic induction. The authors found that TXA administration during PCNL resulted in reduced blood transfusion rate, and higher stone free rates in the immediate postoperative period and at 3 months.¹¹

Although HoLEP is one of the few surgical options recommended by the AUA for patients at high risk of bleeding due to its excellent hemostatic properties, for patients undergoing same-day discharge, hematuria is often the rate limiting factor. Currently, no studies have examined the use of TXA during HoLEP. Therefore, we would like to study if the use of TXA during HoLEP will increase our SDD rates.

STUDY ENDPOINTS:

Primary:

- 1) Difference in same-day discharge and same-day catheter removal rates

Secondary:

- 2) Difference in medical events: defined as unplanned ED visit/clinic visit/procedure/admission related to bleeding, clot retention, clot evacuation, need for perioperative transfusion
- 3) Duration of postoperative hematuria
- 4) Difference in operative, enucleation and morcellation times
- 5) Adverse events related to TXA (thrombotic events (DVT, PE, stroke), seizures,

PROCEDURES INVOLVED:

Visit 1 – Screening (Day -45 – Day 0)

- i. Patients will complete:
 - 1) Patient Informed Consent Form,
 - 2) HIPAA form,

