- ii. Investigative site will complete: patient demographics, medical history, Inclusion/Exclusion Criteria
- iii. Randomization and instructions to patients on whether or not to receive TXA

Visit 2 – HoLEP (Day 0)

- iv. Inclusion/Exclusion Criteria to reconfirm eligibility (only if Screening and HoLEP are not on the same day)
- v. Adverse Events secondary to TXA

Catheter Removal (Day 0 or 1)

Assessment of same day discharge and catheter removal rates

Week 1 through resolution of hematuria

The patient will receive a weekly computer generated text from Twilio (secure software integrated to REDCap) asking them to report their hematuria and dysuria after the procedure. It will also ask if they have had any unplanned visits or interventions. This will continue until 12 week post HoLEP survey

Visit 3 – One month follow-up (Day 30)

If patients have already reported resolution of hematuria, they will receive an additional questionnaire 30 days postoperatively to assess for bleeding complications and symptoms.

Visit 4 – Follow-up (12 weeks Post HoLEP)

- vi. Patient will be assessed for BPH symptom related questionnaires in addition to urinary parameters. Will also confirm if there were or were not bleeding or other complications in first 90 days postoperatively.

Early Withdrawal Patients: The investigator will make reasonable attempts to ensure all enrolled patients complete the study.

****If the patient is unable to complete the questionnaires by text, they will be contacted by phone call for questionnaire completion.**

STU#:

The HoLEP procedure is performed in a similar fashion by all surgeons with similar postoperative care plans. Duration of postoperative catheterization is determined by the treating surgeon, with respect to time of surgical case completion, need for inpatient observation, and patient preference. The portions of the case will not be altered regardless of patient being on anticoagulation or not, however the surgeon will not be blinded to the patient's status of anticoagulation therapy, as this knowledge would be paramount in postoperative management if there were complications.

DATA AND SPECIMEN BANKING

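### The weekly text on unplanned visits has two different end points, one of which ties how often bleeding events are asked about to hematuria duration; separately, a 12-week visit is to confirm 90 days

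*Protocol*

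**What the plan says.** All the scheduling text is in the protocol's Procedures Involved section.

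- **Weekly text, end point.** The block is headed "Week 1 through resolution of hematuria". Its closing sentence says "This will continue until 12 week post HoLEP survey".
- **Weekly text, content.** Besides hematuria and dysuria, "It will also ask if they have had any unplanned visits or interventions".
- **Visit 3 (Day 30).** "If patients have already reported resolution of hematuria, they will receive an additional questionnaire 30 days postoperatively". Its purpose is to pick up bleeding complications and symptoms. No such form is described for patients whose hematuria persists.
- **Visit 4 (12 weeks).** "Will also confirm if there were or were not bleeding or other complications in first 90 days postoperatively". This applies to every patient.
- **Fallbacks.** Patients who cannot answer by text are covered: "they will be contacted by phone call for questionnaire completion". Recruitment Methods adds a text follow-up for patients who cannot attend the last visit in person or virtually.
- **End of data collection.** Recruitment Methods keeps patients enrolled to the week-12 visit and collects nothing after the postoperative visit.

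Under Study Endpoints, secondary endpoint 2 includes "unplanned ED visit/clinic visit/procedure/admission related to bleeding", and secondary endpoint 3 is "Duration of postoperative hematuria".

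**The concern.** The weekly text feeds two secondary endpoints. It tracks hematuria (endpoint 3), and it prompts for the unplanned visits and interventions that make up much of endpoint 2. If it stops once hematuria resolves, the prompting for endpoint 2 depends on a post-randomization outcome that the trial compares between arms. Should TXA shorten hematuria, patients in the two arms would be asked about later bleeding events with different frequency. Events after Day 30 would rest on recall at one 12-week contact for early resolvers, and on weekly reports for patients still bleeding.

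Two people setting up the automated messages could program different rules and each be able to cite the protocol.

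The second problem is independent of the first. A visit at 12 weeks, with no data collected after it, is asked to confirm a 90-day period.

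**Working it through.** The protocol states no figure to reproduce here, so the check is to read the lines together and then count contacts.

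**Readings of the weekly text**

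1. Heading: texts stop at resolution.
2. Closing sentence: texts run to the 12-week survey for everyone.
3. Both combined: texts run until resolution, for at most 12 weeks. This removes the verbal conflict but still stops the text at resolution, so it counts the same as reading 1.

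The Day-30 form for resolved patients makes most sense if their texts have stopped. It is called additional, however, which also fits texts that continue. Nothing elsewhere in the protocol settles the matter.

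**Assumptions for the count** (the protocol gives no exact days): first text on Day 7, then one a week; last text at the week of resolution *r* (readings 1 and 3) or at week 11 (reading 2); Day-30 form if 7*r* ≤ 30, that is *r* ≤ 4; final contact on Day 84. The possible text days between Day 31 and Day 83 are 35, 42, 49, 56, 63, 70 and 77, which is seven.

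**Texts stop at resolution**

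- Total contacts = *r* + (1 if *r* ≤ 4) + 1
- Prompts in Days 31-83 = max(0, *r* − 4)
- Longest gap = 84 − 30 = 54 days if *r* ≤ 4; 84 − 7*r* if *r* ≥ 5

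| Week of resolution | Total contacts | Prompts, Days 31-83 | Longest gap (days) |
|---|---|---|---|
| 1 | 3 | 0 | 54 |
| 2 | 4 | 0 | 54 |
| 3 | 5 | 0 | 54 |
| 4 | 6 | 0 | 54 |
| 5 | 6 | 1 | 49 |
| 6 | 7 | 2 | 42 |
| 8 | 9 | 4 | 28 |
| 11 | 12 | 7 | 7 |

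Without the Day-30 form, the longest gap for weeks 1 to 4 would be 84 − 7*r* = 77, 70, 63 and 56 days. The form therefore shortens it by 23, 16, 9 and 2 days. It ensures that everyone is asked around Day 30, but it does nothing for Days 31-83.

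**Texts run to the 12-week survey**

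- Total contacts = 11 + (1 if *r* ≤ 4) + 1 = 13 or 12
- Prompts in Days 31-83 = 7 for everyone
- Longest gap = 7 days

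The only remaining difference between patients is the one Day-30 form.

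**The 90-day window**

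12 × 7 = 84 days, and 90 − 84 = 6 days, or 6/90 = 6.7% of the stated period. No visit window is given.

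**The case against.** The strongest reply is that a heading is only a label and the closing sentence is the operative instruction. On that reading every patient is texted to the survey and almost nothing is left of the problem. This is a fair reading, but the Day-30 form reserved for resolved patients points the other way, and the combined reading also stops at resolution. The ambiguity stands.

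The other objections limit the consequence, and most of them are right:

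- **No patient goes unasked.** The Day-30 form, Visit 4 and the phone and text fallbacks all apply. What is left is a difference in prompting between Day 30 and Visit 4.
- **The events are discrete and hard to forget.** They include emergency visits, admissions and procedures. Perioperative transfusion does not depend on the texts at all. The section on protected health information mentions medical records, though not as a source for endpoint 2.
- **Several conditions must hold for the arms to differ.** The texts must stop at resolution, TXA must change hematuria duration, and the change must affect prompting after Day 30. Shortening hematuria from week 3 to week 1, for example, leaves prompts in Days 31-83 at zero either way. The protocol gives no duration distribution and no rate of late bleeding after resolution.
- **The 84/90-day gap does not bias the comparison.** It falls on both arms alike, and a visit held on or after Day 90 would satisfy both statements.
- **A Day-30 form for unresolved patients adds little.** Under the count above they already receive texts on Days 28 and 35. This is true. The reason for including it is that all patients should answer the same form.

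**Conclusion.** The point holds and is minor. The protocol gives two end points for a text that collects secondary-endpoint data, and a plausible reading makes the prompting for endpoint 2 depend on endpoint 3. On that reading, prompts in Days 31-83 range from 0 to 7 according to when hematuria resolves, and the longest gap ranges from 54 days down to 7. On the other reading, everyone has 7 prompts in that interval.

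These are counts for illustrative patients, not arm means, and they rest on the assumed contact days. Neither the size nor the direction of any between-arm bias can be derived from the protocol. The primary endpoint is not affected.

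The 12-week and 90-day statements are inconsistent by 6 days at the nominal visit date. That leaves the stated window incompletely covered, equally in both arms, unless the visit is held late. Confidence is high for the textual conflict and the day count; it does not extend to a claim that the arms would differ.

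**What to change.** State one schedule for every patient, whether or not hematuria has resolved: the same weekly text from week 1 to the 12-week survey and the same Day-30 questionnaire. Change the block heading to match. Then choose one complication window: either define it as 84 days, or set the final contact at Day 90 or later and align the end of data collection in Recruitment Methods.

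The cost is wording and REDCap/Twilio settings.

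- **If stopping at resolution was intended,** the extra texts number 11 − *r*: 9 for a week-2 resolver, and 5 plus one Day-30 form for a week-6 resolver. The maximum is 10 per patient (*r* = 1), so at most 110 × 10 = 1,100 automated texts across the trial.
- **If texting to 12 weeks was intended,** the only addition is one Day-30 form for each patient unresolved at that point.

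The drawback is slightly more questionnaire burden for patients without symptoms.

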Secondary outcomes will assess bleeding complications (defined as unplanned ED visit/clinicvisit/procedure/admission related to bleeding, clot retention, clot evacuation, need for perioperative transfusion) between patients who receive TXA vs. those do not. We will also assess differences in perioperative complications associated with TXA including but not limited to: deep venous thrombosis, pulmonary embolism, cerebrovascular events, between the groups. We will also assess for the duration of postoperative hematuria between groups. Additionally, we will assess for differences in operative times between the groups.

We anticipate that there may be up to a 25% increase in SDD rates in those who receive TXA vs. those who do not.

BACKGROUND:

Holmium Laser Enucleation of the Prostate (HoLEP) is a size-independent treatment option for benign prostate hypertrophy (BPH) as recommended by the American Urological Association (AUA) Guidelines.¹ Furthermore, HoLEP is one of the few surgical options that is recommended by the AUA for patients on active anticoagulation given its superior hemostatic properties.¹ [name] research team has previously shown that same-day catheter removal and same-day discharge (SDD) was successful in approximately 87% of patients.² This study was performed in a limited cohort of 207 patients. [name] was recently recruited to Northwestern Medicine to introduce HoLEP to Chicago. Our current SDD rate is approximately 60%. Factors limiting discharge are primarily related to the degree of hematuria and patient anxiety.

Tranexamic Acid (TXA) is an indirect fibrinolytic inhibitor and was discovered in the early 1960s.³ Although it was initially only used in women with heavy menstrual blood loss and those with hereditary bleeding disorders, it is now widely used in trauma situations and orthopedic, cardiac, otolaryngologic, and obstetric surgeries as it is cheap, safe, and effective.³ Oral, IV, topical and combined methods of TXA administration also reduced blood loss and risk of transfusion compared to placebo for patients undergoing total hip arthroplasty.⁴ TXA is safe, but high doses of TXA (80-100 mg/kg) or TXA use in those with poor renal function have been associated with an increased risk of seizures.⁵ While there is no clear evidence of increased risk of thromboembolic events⁶, it should be used cautiously in those with a history of embolic events, those on hormonal contraceptives.⁷

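### How bleeding events are ascertained depends on hematuria status: the Day 30 form goes only to men who have reported resolution, and the end of the weekly texts is stated in two ways

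*Protocol*

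**What the plan says.** Follow-up after discharge is set out in the protocol under Procedures Involved.

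- **Weekly text.** Patients get an automated message "asking them to report their hematuria and dysuria after the procedure". On unscheduled care the entry adds: "It will also ask if they have had any unplanned visits or interventions". The entry's heading gives the period as "Week 1 through resolution of hematuria", while its last sentence says "This will continue until 12 week post HoLEP survey".
- **Visit 3, Day 30.** The entry reads: "If patients have already reported resolution of hematuria, they will receive an additional questionnaire 30 days postoperatively to assess for bleeding complications and symptoms". No other group is named as receiving this form.
- **Visit 4, week 12.** For all patients: "Will also confirm if there were or were not bleeding or other complications in first 90 days postoperatively".
- **Back-up.** "If the patient is unable to complete the questionnaires by text, they will be contacted by phone call for questionnaire completion".

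Study Endpoints lists bleeding-related medical events and the duration of hematuria as separate secondary endpoints. The Objectives make the second a comparison between arms: "We will also assess for the duration of postoperative hematuria between groups".

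**The concern.** Whether a man receives the Day 30 form depends on something that happens after randomisation and that the treatment may influence. The form asks about bleeding complications, which are compared between arms. The condition for sending it is resolution of hematuria, whose duration is also compared between arms. One secondary endpoint thus decides how another is ascertained. If the arms differ in how soon hematuria resolves, they will differ in who is asked what, and a difference in reported bleeding events could partly reflect that.

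Two features add to this. First, the weekly text and the Day 30 form are not stated to ask the same questions: the text covers hematuria, dysuria and unscheduled care, while the form is described as directed at bleeding complications and symptoms. Second, no placebo is described (one group simply receives no TXA) and patients are told their allocation at screening. Reports come from men who may know their arm, which makes identical questioning more important.

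Men who do not answer the texts are affected too. Without a report of resolution they do not meet the Visit 3 condition. The phone back-up helps a man complete a questionnaire he is due; it does not make him due for this one.

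**Working it through.** The plan gives no figure on this point, so there is none to reproduce. The check counts scheduled contacts about bleeding before the week 12 visit, by when resolution is reported, under each reading of the weekly text entry.

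**Inputs.** From Procedures Involved: texts are weekly from week 1; the Day 30 form is sent only if resolution has already been reported. Assumptions: one text in each of weeks 1 to 12, so four fall by Day 30; resolution is reported at the text of the week shown.

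**Formula.** Contacts = weekly texts sent + 1 if resolution was reported by Day 30.

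| Resolution reported | Texts stop at resolution (heading) | Texts to week 12 for all (body) |
|---|---|---|
| Week 2 | 2 + 1 = 3 | 12 + 1 = 13 |
| Week 4 | 4 + 1 = 5 | 12 + 1 = 13 |
| Week 8 | 8 + 0 = 8 | 12 + 0 = 12 |
| Never | 12 + 0 = 12 | 12 + 0 = 12 |

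If the week 12 survey replaces the twelfth text, each count that includes 12 texts falls by one and the pattern stays the same.

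- **Heading's reading.** Both instrument and frequency depend on the outcome. Men who resolve early have fewer contacts. After the Day 30 form they have nothing scheduled until week 12, a gap of 12 × 7 − 30 = 54 days. Men still bleeding are texted weekly but never get the Day 30 form.
- **Body's reading.** Frequency is nearly equal, 13 against 12. The remaining difference is the one extra bleeding questionnaire, which only men resolved by Day 30 receive.

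**How far form receipt could differ by arm.** The documents give no resolution rates, so these are assumptions, as is equal allocation (110 / 2 = 55 per arm).

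- If 85% (TXA) and 65% (no TXA) have reported resolution by Day 30: 55 × 0.85 = 46.75 and 55 × 0.65 = 35.75, so about 47 against 36 get the form and about 8 against 19 do not.
- If 90% and 85%: 55 × 0.90 = 49.5 and 55 × 0.85 = 46.75, so about 50 against 47 get it.

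These figures count forms sent. They do not measure events missed or added, and so do not measure bias.

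**The case against.** The strongest defence is that Visit 3 is a catch-up. Read with the heading above it, the additional form keeps contact with men whose texts have ended, while men still bleeding stay under weekly contact. Most of the bleeding endpoint is unplanned care, which the weekly text asks about, and the week 12 visit covers the first 90 days in everyone. No endpoint event can be named that would be caught in resolved men and necessarily lost in the others.

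Much of this stands. A reader might infer that men still bleeding miss the only scheduled bleeding assessment before week 12. The documents do not support that: under either reading those men are still receiving weekly texts around Day 30.

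A reader might also infer that the scheme adds reported events to the arm that resolves sooner. That is not established either. It is plausible if texts run to week 12 for all. If texts stop at resolution, the thinner follow-up falls on early resolvers and the effect could go the other way.

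The defence does not remove the problem. The catch-up reading relies on the heading and conflicts with the body of the same entry. If it is right, it confirms that the type and frequency of questioning follow the outcome. The week 12 check is a real safeguard, but it asks about 90 days at once, and the prospective reports behind it would still have been gathered unevenly.

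**Conclusion.** The point holds in a limited form. The Day 30 questionnaire is conditional on reported resolution, and heading and body conflict on when the weekly texts stop. Ascertainment of bleeding events therefore depends on hematuria status: in instrument under both readings, and substantially in frequency under the heading's reading (3 to 5 contacts for men resolved at weeks 2 to 4, against 12 for men never resolved).

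The direction and size of any bias in the between-arm comparison are unknown. It would be nil if resolution by arm were the same and reporting otherwise alike. Equal resolution is not the only route to no bias: there would also be none from the form itself if it yielded no event beyond those found by the texts and the week 12 check.

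The contact counts rest on one text per week for 12 weeks. The split of forms by arm rests on assumed resolution rates and equal allocation. This is a moderate point about a secondary endpoint. Same-day discharge and catheter removal, the primary endpoint, are settled before any of these contacts and are not affected.

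**What to change.** 1. Delete the condition in Visit 3. Send the same Day 30 questionnaire to every randomised patient, whatever his hematuria status or earlier response to texts, with the phone back-up already provided.
2. Reconcile the heading and body of the weekly text entry so that texts follow one schedule to week 12 for all patients. Without this, deleting the condition would still leave contact frequency dependent on the outcome.
3. State that the weekly, Day 30 and week 12 reports are used together for the between-arm comparison of bleeding events, so that the prospective weekly reports are not set aside in favour of longer recall.

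For the Day 30 form the cost is one clause deleted, one REDCap trigger changed, one extra automated form for unresolved patients and a few more phone calls. If the texts currently stop at resolution, running them to week 12 also means further automated messages to men who have resolved; if they already run to week 12, only the heading changes.

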After the patient completes their pre-surgical enrollment paperwork in the clinic, they will then be met in a private room away from the treating physicians by a qualified research coordinator who will discuss their potential enrollment and complete any research paperwork. Some patients may be approached via telephone with virtual consent.

Therefore, the initiation of enrollment will begin at the time of the office consultation visit. The patient will remain enrolled until she/he has completed the post-procedure follow up clinic/virtual visit at week 12. Data will not be collected beyond when the patient is seen at the postoperative clinic visit. If the patient is unable to have a physical or virtual visit, a text follow-up will be performed.

After consenting, patients will be randomized to one of two groups.

Group 1 (control): Receive intraoperative 1g TXA

Group 2 (experimental): No TXA

Randomization to **Group 1** or **Group 2** will be allocated through REDCap.¹² The stratified randomization list will be created and provided by the study statistician before the start of patient recruitment.

COMPENSATION FOR PARTICIPATION IN RESEARCH ACTIVITIES

Patients will not be compensated for participating in this research.

WITHDRAWAL OF PARTICIPANTS

If a subject wishes to withdraw from the study, he/she may do so by verbal request to the research team. A subject may be withdrawn from the study by a physician-investigator if determined to be in the subject's best interest for medical reasons.

RISKS TO PARTICIPANTS

The risks in this study are no greater than the risks incurred during a HoLEP. AUA and EAU guidelines support HoLEP as a size independent treatment option for BPH.

Common side effects of TXA are nausea, vomiting, diarrhea, and muscle pain.

POTENTIAL BENEFITS TO PARTICIPANTS

Patients in the TXA arm may have higher rates of success with same day discharge and same day catheter removal.

DATA MANAGEMENT AND CONFIDENTIALITY

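### No provision masks the surgeon, discharge staff or patients to TXA, although surgeon judgement and patient preference feed the primary endpoint

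*Protocol*

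**What the plan says.** All of the relevant text is in the protocol.

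- **Primary endpoint** (Study Endpoints): "Difference in same-day discharge and same-day catheter removal rates".
- **Arms** (Recruitment Methods): Group 1 is to "Receive intraoperative 1g TXA". The comparator is "Group 2 (experimental): No TXA". No placebo is mentioned. (The control and experimental labels look reversed; that is a separate matter.)
- **Patients** (Procedures Involved, Visit 1, item iii): "Randomization and instructions to patients on whether or not to receive TXA".
- **Catheter decision** (Procedures Involved, paragraph on the HoLEP procedure): "Duration of postoperative catheterization is determined by the treating surgeon, with respect to time of surgical case completion, need for inpatient observation, and patient preference".
- **Blinding** (same paragraph, the only statement on the subject): "the surgeon will not be blinded to the patient's status of anticoagulation therapy", with the reason "as this knowledge would be paramount in postoperative management if there were complications".

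Four other statements bear on the point. The same paragraph says that the surgeons operate alike and that their postoperative care plans resemble one another. The exclusion criteria require catheter removal and a voiding trial at the study hospital. The Objectives and Background name hematuria as the main limit on same-day discharge, and the Background adds patient anxiety. Recruitment Methods has the coordinator meet patients away from the treating physicians, which covers enrolment only.

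**The concern.** The primary endpoint is partly a judgement. If the person judging knows that TXA was given and expects less bleeding, the catheter may come out sooner at the same degree of hematuria, or a patient without TXA may be kept overnight. Patients who know their arm may also feel more or less ready to leave. Preference is a listed ground for catheter duration, and anxiety is a named obstacle to discharge. Either route produces a difference between arms that cannot be told apart from a drug effect.

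The Background makes the question concrete. It reports a randomized TURP trial of 136 men in which TXA reduced blood loss but did not shorten stay or catheter time. If this trial finds more same-day discharges, readers will ask whether the drug or the knowledge of the arm produced them, and an unmasked design cannot answer. An analysis plan cannot supply this later, because masking belongs to the conduct of the trial.

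**Working it through.** **Step 1: who could know the arm.**

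| Party | What the protocol provides | Consequence |
|---|---|---|
| Patient | Item iii: instructed at Visit 1, which may fall up to 45 days before surgery | Knows the arm as written |
| Surgeon | TXA or nothing during the surgeon's own case; no placebo; no masking provision | Free to know; the patient can also tell |
| Recovery and discharge staff | No provision | Free to know |

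**Step 2: what the blinding sentence covers.** The Objectives describe TXA as promoting clotting, so it is not an anticoagulant. Read literally, the sentence concerns background anticoagulants and gives no reason for leaving the surgeon unmasked to TXA. Read as a slip for TXA, it expressly unmasks the surgeon. Neither reading provides masking.

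**Step 3: how judgement enters the endpoint.** There are three grounds for catheter duration. Case completion time is a clock fact. Preference belongs to the patient, who knows the arm. The need to observe the patient in hospital is mainly the surgeon's judgement, and it is also the link to discharge. No hematuria threshold is written for any of them.

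**Step 4: illustration of size.** The protocol gives no figure for bias, so there is none to reproduce. Its sample size is stated without alpha, power or allocation ratio and serves here only as an input.

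Inputs:
- N = 110 (Study Summary). Assumed 1:1, so n = 110/2 = 55 per arm.
- Same-day discharge about 60% (Objectives, Background), taken for both arms because the drug is assumed to be null.
- Two-sided 5% pooled z test (assumed).
- Shift in the TXA arm due only to knowledge of the arm (assumed; shown as a range).

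With x_T and x_C same-day discharges and p̄ = (x_T + x_C)/110:

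z = [(x_T − x_C)/55] / √[p̄(1 − p̄)·2/55]

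P(false result favouring TXA) = sum of Bin(x_C; 55, p_C) × Bin(x_T; 55, p_T) over all pairs with z > 1.96.

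| Shift in TXA arm | TXA patients moved (shift × 55) | Share of the 40% who would otherwise stay | P(false result favouring TXA) |
|---|---|---|---|
| 0 | 0 | 0 | 2.5% |
| +5 points | 2.75 | 12.5% | 8.0% |
| +10 points | 5.5 | 25% | 20.1% |
| +15 points | 8.25 | 37.5% | 39.9% |

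If knowledge of the arm acts in both directions, +5 points with TXA and −5 without gives 18.6%.

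As a scale: with 33/55 (60%) discharged without TXA, 43/55 with TXA is the smallest significant count. There p̄ = 76/110 = 0.691 and z = 0.1818/√(0.691 × 0.309 × 2/55) = 0.1818/0.0881 = 2.06. At 42/55, z = 0.1636/0.0888 = 1.84. A gap of 10 patients therefore decides the trial.

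**The case against.** Several points on the other side stand and limit the claim.

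- **A reader might infer that the protocol declares the surgeon unmasked to TXA.** It does not. This is inferred from the untreated comparator, intraoperative dosing, item iii and the absence of any masking provision. The intended scope of the anticoagulation sentence cannot be settled from the text.
- **A reader might infer that the surgeon's discretion alone sets the primary endpoint.** It is written only for catheter duration, one half of the endpoint, and reaches discharge through the need for observation. The voiding trial adds a more objective step, hematuria is acknowledged as the main limiting factor, and the care plans are said to be alike. These mitigate only in part: the care plans are described without a rule, and a voiding trial does not fix when the catheter is first removed.
- **A reader might extend the point to operative, enucleation and morcellation times.** The same paragraph says that the procedure is uniform and that the case is not altered for anticoagulation status. If that wording was meant for TXA, the commitment carries over as well, so the text does not support a separate claim on these times.
- **The error rates are illustrative.** Any unmasked trial with a partly judged endpoint shows such inflation under an assumed shift. Nothing in the document gives the size or direction of a shift here.
- **An open-label comparison without placebo is a legitimate design choice.** That is so, but no reason is given for leaving TXA unmasked. The Background itself reports a double-blind, placebo-controlled trial of 1 g intravenous TXA given at anesthetic induction in PCNL, so masking this drug has been done. The stated need to know in case of complications can be met by unmasking on request.

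**Conclusion.** The point holds as a weakness in design and wording. The comparison has no placebo, patients are told their arm, nobody is masked to TXA, and the catheter half of the primary endpoint rests partly on surgeon judgement and patient preference without a stated hematuria criterion. Knowledge of the arm could therefore shift the result. Under the assumptions stated (1:1 allocation, 60% in both arms, null drug, two-sided 5% test), shifts of 5 to 15 points in the TXA arm would raise the false-positive risk in favour of TXA from 2.5% to between about 8% and 40%. Those figures show sensitivity; they do not estimate the bias in this trial. That the protocol states TXA unmasking outright, or that the surgeon alone decides discharge, is not supported.

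**What to change.** 1. **Procedures Involved and Recruitment Methods:** state that REDCap releases the allocation to the anesthesia team only, and that the surgeon and the recovery and discharge staff remain masked to TXA until the catheter and discharge decisions are recorded, with unmasking on request for a complication.
2. **Visit 1, item iii:** amend it so that patients are not told their arm until those decisions are recorded. Without this, patients can act on the allocation or pass it on, and the first change is easily defeated.
3. **Anticoagulation sentence:** say whether it covers background anticoagulants only, and that it does not extend to the TXA allocation.
4. **Catheter and discharge decision:** have the clinical team reconcile the discretionary sentence with the statement that care plans are alike, so that one rule of their choosing applies in both arms. Record the reason for each overnight stay.

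The cost is protocol wording, REDCap access rights, an instruction to anesthesia and one added data field. No patients or visits are added; the document does not allow the staff time to be costed. Masking without a placebo remains imperfect, and a surgeon managing a bleed may need to ask for the allocation. Each such unmasking should be logged.
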